13. MANAGEMENT OF TOXICITIES AND COMPLICATIONS

13.A. Toxicity Grading

Toxicity grading will be evaluated according to the current guidelines in NCI Common Toxicity Criteria version 4.0.⁷⁷ The full text of the NCI CTCAE is available online at: <http://evs.nci.nih.gov/ftp1/CTCAE/About.html>.

13.B. Regimen Related Toxicity

If the patient develops excessive Toxicity attributable to one or more component of the regimen, the patient will not receive additional study treatment and a treatment of corticosteroids will be given, if clinically indicated (please refer to **Section 13.C**). Excessive toxicity will be considered when a non-pre-existing Grade 3 or higher toxicity develops after the start of treatment with the following exceptions:

13.B.1. Expected toxicities attributable to anti-PD-L1 (Avelumab) infusions and considered exceptions to criteria for discontinuation include:

1. Infusion-related reactions (see **Section 13.C** for management):
 - i. Transient (\leq 6 hours) Grade 3 CRS, flu-like symptoms or fever, which is controlled with medical management.
 - ii. Transient (\leq 24 hours) Grade 3 fatigue, local reactions, headaches, nausea, emesis that resolved to \leq Grade 1.
 - iii. Single laboratory values out of normal (excluding Grade \geq 3 liver function tests increase) that are unlikely related to Avelumab according to the investigator, do not have a clinical correlate, and resolve to \leq Grade 1 within 7 days with adequate medical management.
 - iv. Urticaria lesions responding to antihistaminics (Grade 2)
 - v. Allergic reaction (flushing or rash) responding to antihistaminic treatment (Grade 2).
2. Tumor flare phenomenon defined as local pain, irritation, or rash localized at sites of known or suspected tumor.

3. Tumor-lysis syndrome: If symptoms of tumor lysis occur after the Avelumab infusions they will be managed according to best clinical practice (see **Section 13.C.4**). Tumor lysis will not constitute a reason to discontinue the Avelumab infusions.
4. Change in ECOG PS to ≥ 3 that resolved to ≤ 2 within 14 days (infusions should not be given on the following cycle if the ECOG PS is ≥ 3 on the day of the Avelumab administration).

13.B.2. Expected toxicities attributable to **localized radiation** of pre-existing symptomatic metastasis and considered exceptions to criteria for discontinuation include:

- i. Non-life-threatening - diarrhea (i.e. 4-6 stools over baseline stools a day)

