- ii. Target organ inflammatory responses resulting in Grade 3 or 4 toxicities that return to baseline within 4 weeks. For example: elevated lipase and/or amylase after radiation to a pancreatic lesion; or elevated transaminases after radiation to a liver lesion.
- iii. Hyperglycemia (Grade 3) lasting <14 days.
- iv. Dry skin, skin pain, and erythema lasting <14 days.
- v. Single laboratory values out of normal that according to the investigator do not have a clinical correlate and resolve to \leq Grade 1 within 7 days with adequate medical management.

13.B.3. Expected toxicities attributable to **intraleisional IFN β -1B injections** and considered exceptions to criteria for discontinuation include:

- i. Non-life-threatening infections (i.e. absence of hemodynamic compromise requiring pressor support and non-opportunistic infection).
- ii. CRS Grade 3 or less, including but not limited to asthenia, flu-like symptoms, myalgia, lymphopenia, and rigors.
- iii. Target organ inflammatory responses resulting in Grade 3 or 4 toxicities that resolve within 4 weeks. For example: elevated lipase and/or amylase after injection to a pancreatic lesion; or elevated transaminases after injection to a liver lesion.
- iv. Single laboratory values out of normal that according to the investigator do not have a clinical correlate and resolve to \leq Grade 1 within 7 days with adequate medical management.

13.B.4. Expected toxicities attributable to **T-cell infusions** and considered exceptions to criteria for discontinuation include:

- i. CRS Grade 3 or less, including but not limited to asthenia, flu-like symptoms, myalgia, lymphopenia, and rigors.
- ii. Skin rash or erythroderma (Grade 3 toxicity) lasting for <7 days.

- iii. Hypoxemia requiring continuous oxygen <72 hours, but not requiring mechanical ventilation or intubation.
- iv. Fever that resolves within 36 hours of the T-cell infusion.
- v. Lymphopenia (lymphocytes <500) that resolves to baseline levels (pre-therapy) within 4 weeks.
- vi. Single laboratory values out of normal that according to the investigator do not have a clinical correlate and resolve to ≤ Grade 1 within 7 days with adequate medical management.

13.C. Management of Symptoms During Avelumab Infusions

13.C.1. Special precautions

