Management will be by **decreasing the rate of infusion and/or appropriate supportive care** such as:

- Acetaminophen or Demerol for fever and chills. (All subjects who develop fever or chills should have a blood culture drawn).
- Acetaminophen for headache.
- Diphenhydramine for nausea and vomiting.
- Fluid administration for hypotension.
- Supplemental oxygen for hypoxemia.

13.D.2. More severe reactions occurring during the 1-2 hour infusion would include symptoms such as:

- Hypotension with systolic BP <90 mm Hg and >20 mm Hg below baseline
- Tachycardia with HR >130 and >30 above baseline.
- Tachypnea with RR >32 and >10 above baseline.
- Hypoxemia with O₂ saturation of <88% and >5% fall from baseline.

Management will be by **terminating the infusion and administering supportive medical care**.

- If patient responds to supportive care by normalization of vital signs or resolution of hypoxemia and PI deems it safe to continue, the infusion will be restarted at slower rate.
- If the patient does not respond by normalization of vital signs or hypoxemia after supportive care alone, **methylprednisolone to ablate the infused T cells will be administered as per Section 13.E.**

13.D.3. Any unexpected severe toxicity (see Section 13.B) occurring in the first 24 hours (due to the T-cell infusion and not attributable to a non-infusion-related cause).

Management will be by **supportive medical care and methylprednisolone will be administered as per Section 13.E.**

13.D.4. Delayed toxicities secondary to T-cell infusions

Although unlikely, it remains possible that the infusion of MCPyV TAg-specific T cells will result in delayed toxicities related to the recognition of tumor tissue. It is anticipated that the symptoms and signs will occur within hours to four weeks after completion of the T-cell infusion.

Any toxicities requiring treatment discontinuation (see Section 13.B) occurring within 4 weeks of study treatment (potentially due to the T-cell infusion and not attributable to a non-infusion-related cause) **will be managed by supportive care and MP will be administered as per Section 13.E.**

13.E. Management of Severe Treatment-related Toxicities with Corticosteroids

- i. The patient will receive corticosteroids if treatment-related toxicity warranting ablation of T cells is observed.
- ii. The patient will be hospitalized for the first 48 hours for monitoring. The following dose schedule is recommended:

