18. STATISTICAL CONSIDERATIONS

The **primary objective** of this trial is to assess and compare the safety and potential efficacy associated with treating patients who developed metastatic MCC by combined MHC up-regulation and anti-PD-L1 antibody treatment (Group 1); and combined MHC up-regulation, anti-PD-L1 antibody treatment, and adoptive transfer of MCPyV TAg-specific polyclonal autologous CD8⁺ T cells (Group 2). The treatment for each group will be considered to have an acceptable safety profile, if the observed toxicity rate is consistent with a true rate that does not exceed 30%, whereas toxicity is defined in **Section 13**. The potential efficacy of treatment within each group will be assessed primarily by examining the time from first to second metastasis. Among 49 patients who would be considered eligible for this trial and who received standard treatment (localized radiation or chemotherapy) at UW, the median time to second metastasis was an estimated 200 days (**Figure 146**). This is the benchmark that we shall use in the current trial for assessment of potential efficacy.

[figure not shown]

Figure 146. Observed and predicted times to second metastasis

A total of 20 patients will be treated in the trial, including 10 in each of Groups 1 and 2 as long as the level of safety is deemed to be acceptable. This number was not derived based on any formal statistical considerations; rather, it is a number that is a compromise between the number of patients that can be enrolled in a reasonable time frame and the number of patients whose treatment will provide enough information to gain a preliminary assessment of efficacy. From our database of over 850 patients, we are in active contact with ~300 living MCC patients. Approximately 120 new patients are recruited each year to our cohort. One-third of MCC patients will have a first metastasis within 3 years of diagnosis. Each year, approximately 40 patients in our cohort experience a first metastasis. Because we now have tetramers that cover >80% of MCC patients based on their HLA alleles, we anticipate that generation of functional tetramer-positive MCPyV-specific T cells from the peripheral blood will be feasible on a sufficient number of cases so that we can readily meet targeted enrollment of four cases per year.

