The study will be suspended pending a review by the DSMB if there is ever sufficient evidence to suggest that the true toxicity rate exceeds 30% in any group. In terms of toxicity of conventional therapy, fractionated ionizing radiation of 30-60Gy is typically effective in controlling the target MCC lesion, but it is commonly associated with transient grade ≤ 3 local toxicities such as mucositis and erythema, depending on the target site. However, radiation therapy cannot be used to repetitively control multiple recurrences.⁸¹ The rate of grade ≥ 3 toxicities associated with platinum-based chemotherapy regimens for the systemic treatment of MCC is approximately 30% to 40%.⁸² Thus, in order not to exceed the toxicity rate induced by standard systemic treatment, enrollment to any group will be suspended if evidence suggests that the true toxicity rate exceeds 30%. Sufficient evidence will be taken to be an observed proportion of toxicities for which the associated lower 80% confidence limit exceeds 30%. Operationally, this limit will be met if any of the following proportions is observed: 2/2-3, 3/4-5, 4/6-8, 5/9-10. Based on this rule, if the true probability of toxicity is 10%, the probability of suspending one group after 10 patients is approximately 0.03. If the true probability of toxicity is 50%, the probability of suspension is 0.76.

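### A T-cell infusion reaction that 13.D.2 and 13.E manage with steroid ablation of the T cells can also be a 13.B.4 exception, and so go uncounted in the Section 18 suspension rule

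*Combined protocol and SAP*

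**What the plan says.** Section 13.B gives the definition: "Excessive toxicity will be considered when a non-pre-existing Grade 3 or higher toxicity develops after the start of treatment with the following exceptions". The exceptions come in four lists, one per treatment component. The T-cell list, 13.B.4, presents its items as expected toxicities "and considered exceptions to criteria for discontinuation include". Two of them matter here:

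- Item iii: "Hypoxemia requiring continuous oxygen <72 hours, but not requiring mechanical ventilation or intubation". It has no saturation floor and no grade limit.
- Item i: "CRS Grade 3 or less, including but not limited to asthenia, flu-like symptoms, myalgia, lymphopenia, and rigors". It has no time limit.

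Neither item sets aside an event that is treated with steroids.

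Section 13.D.2 covers the more severe reactions during the T-cell infusion itself, among them "Hypoxemia with O₂ saturation of <88% and >5% fall from baseline". If supportive care works, the infusion may be restarted at a slower rate. If it does not, "methylprednisolone to ablate the infused T cells will be administered", with the schedule in 13.E. The heading of 13.E places these events among severe treatment-related toxicities.

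Section 18 calls a group's safety acceptable "if the observed toxicity rate is consistent with a true rate that does not exceed 30" per cent, and says that toxicity is defined in Section 13. A group is suspended at 2 of 2-3, 3 of 4-5, 4 of 6-8 or 5 of 9-10 patients with toxicity. Section 16.C has the DSMB judge excessive toxicity by 13.B.

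**The concern.** The same reaction receives two classifications. Under 13.D.2 and 13.E it is severe enough that the study product is deliberately destroyed. Under 13.B.4 it is an expected event that does not make the toxicity excessive.

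This matters because toxicity is a primary endpoint (Section 5.A) and the Section 18 boundary is the only numerical safety stop. A reaction to the T cells that ends in their ablation is what a stop in Group 2 should register.

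The mismatch looks like an oversight. Section 13.B itself pairs excessive toxicity with corticosteroids, and 13.D.3 and 13.D.4 tie methylprednisolone to toxicities as set out in 13.B. Only 13.D.2 orders ablation without that link.

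**Working it through.** **Step 1: can one patient meet both provisions?** Follow a Group 2 patient through the text.

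| Course of the event | Provision | Classification |
|---|---|---|
| Saturation below 88% and a fall of more than 5% during the infusion | 13.D.2 | More severe reaction |
| No normalization after supportive care alone | 13.D.2 | Steroids to ablate the T cells |
| Steroid course given | 13.E | Severe treatment-related toxicity |
| Off continuous oxygen before 72 hours, never ventilated or intubated | 13.B.4.iii | Exception |

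Nothing in one row excludes another, so the overlap exists. The hypoxemia route needs no further labelling. A hypotensive reaction under 13.D.2 overlaps only if it is recorded as CRS of Grade 3 or less (13.B.4.i). The exception has an effect only where the event is Grade 3 or higher, since a lower grade would not be counted under 13.B in any case.

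**Step 2: does the exception reach the suspension count?** Section 18 sends the reader to Section 13 for the meaning of toxicity. Section 13.B holds the only such definition there, and Section 16.C cites 13.B for the DSMB's judgement. No passage says that an event leading to T-cell ablation counts despite 13.B.4. The natural reading is therefore that it does not count.

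**Step 3: reproduce the plan's own figures.** Input: the printed boundary, checked after every patient up to 10. Section 18 states suspension probabilities of about 0.03 at a true rate of 10% and 0.76 at 50%. A cumulative count cannot fall, so it is enough to check the last sample size in each range: at least 2 by patient 3, 3 by patient 5, 4 by patient 8, 5 by patient 10.

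At p = 0.5:

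- By patient 3: P(at least 2 of 3) = 0.500. Remaining: 0 events 1/8, 1 event 3/8.
- By patient 5: add 3/8 × 1/4 = 0.094, total 0.594. Remaining: 0 events 1/32, 1 event 5/32, 2 events 7/32.
- By patient 8: add 7/32 × 1/2 + 5/32 × 1/8 = 0.129, total 0.723. Remaining with exactly 3 events: (7/32)(3/8) + (5/32)(3/8) + (1/32)(1/8) = 37/256.
- By patient 10: add 37/256 × 1/4 = 0.036, total 0.759.

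At p = 0.1 the same steps give running totals of 0.028, 0.030, 0.032 and 0.032 (0.0324 unrounded). Both stated figures are reproduced. The arithmetic of the rule is sound on its own boundary. The question is only which events enter it.

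**Step 4: what does one uncounted patient do?** Compare the count with and without that patient:

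| Patients treated | Counted | Not counted |
|---|---|---|
| 3 | 2 of 3: suspend | 1 of 3: continue |
| 5 | 3 of 5: suspend | 2 of 5: continue |
| 8 | 4 of 8: suspend | 3 of 8: continue |
| 10 | 5 of 10: suspend | 4 of 10: continue |

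Each row assumes that the boundary was not crossed earlier. The first row depends on the printed boundary: by the Clopper-Pearson method the one-sided 80% lower limit for 2 of 3 is about 0.287, just under 30%. The other rows meet the criterion by that method as well.

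**The case against.** Four points on the other side have force.

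- **The overlap is narrow.** Section 13.D.2 applies only during the infusion, requires both the saturation limit and the fall, and orders steroids only for patients who do not respond. The same patient must then be off oxygen within 72 hours without ventilation. This stands and limits the size of the point.
- **The link to Section 18 is a reading.** Section 18 cites Section 13 as a whole, and the lists are worded as exceptions to discontinuation, which concerns the individual patient. Section 16.C also distinguishes individual-patient criteria from trial-level ones. The text does not settle the matter outright. But the lists also complete the 13.B definition that 16.C cites, and if another meaning was intended Section 18 does not give it.
- **The DSMB sees these events anyway.** It reviews all Grade 3 or higher toxicities and SAEs with no exception list at that step, and may meet ad hoc. So the event would not be hidden. What is lost is its weight in the prespecified trigger; the one fixed meeting comes after four Group 2 patients.
- **Treating a reaction acutely and classing it as expected are different functions.** That is true, but a plan that does both should say which one governs the count.

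A reader might also infer that an ablated patient would simply be infused again. The documents do not support that. Section 13.G lets the investigator end therapy when more infusions are not in the patient's interest, and Section 6 makes repeat courses conditional on continuing clinical eligibility.

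**Conclusion.** The contradiction between 13.B.4 and 13.D.2/13.E is in the text and is unresolved. On the natural reading it carries into the suspension count. Its size is one patient at a time: the documents give no frequency for such reactions, but in a group of 10 one patient is enough to decide suspension. The conclusion assumes that Section 18 means the 13.B definition of toxicity and that the event is graded 3 or higher.

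Two stronger readings are not supported:

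- A reader might infer that the rule loses much of its 0.76 chance of suspension at a 50% toxicity rate. That would require a large share of affected patients to have only exempt events. The documents give no such share, and the subset at issue here is a small part of everything exempted.
- A reader might infer that the 30% limit, set "in order not to exceed the toxicity rate induced by standard systemic treatment", compares an excepted count with an unexcepted one. Section 18 quotes a 30% to 40% rate of Grade 3 or higher toxicity for platinum regimens and does not say how it was counted. Silence about exceptions does not show that there were none.

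**What to change.** Reconcile 13.B.4, 13.D.2, 13.E and Section 18 so that each event has one classification. This does not require choosing or changing any clinical rule.

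In Section 18, add one counting sentence: a Grade 3 or higher reaction attributed to the T cells, for which 13.E steroids are given to ablate them, enters the suspension numerator even if it is on the 13.B.4 list.

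Keep the sentence that narrow. Section 13.C.5 also sends avelumab immune-related events to 13.E with no grade floor. Counting every event given 13.E steroids could therefore admit avelumab events below Grade 3, which the definition in 13.B does not cover.

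The cost is protocol wording. Grade 3 or higher events are already recorded (12.C), and 13.E already requires T-cell assays around the start of steroids, so these cases are identifiable. The boundary and its stated operating characteristics stay as they are. The downside is a slightly higher chance of a pause for DSMB review, which cannot be quantified without a frequency for these reactions.
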